1.1. Hypotheses

The primary hypothesis of this study is that early substitution of subcutaneous abatacept for belatacept in an immunosuppressive regimen will effectively and safely allow for a minimization of exposure to CNI while preserving renal function and achieving acceptable alloimmune events.

1.2. Primary Objective

The coprimary objectives of this study are to:

- Evaluate the effectiveness (freedom from rejection) and safety (such as adverse events, serious adverse events, infections, cardiovascular, metabolic side-effects) of a regimen substituting subcutaneous abatacept for belatacept as a means of improving long-term graft function by reducing exposure to calcineurin inhibitor-based immunosuppression.
- Assess the logistics of subcutaneous delivery of abatacept and the accrual and retention of study subjects during the first year after transplant to potentially inform the potential design and conduct of further clinical development including Phase II and/or Phase III trials.

1.3. Secondary Objectives

Secondary objectives also include:

- Additional assessment of effectiveness (graft function, DSA).
- Measurement of the levels, stability and trajectory of renal function (eGFR) in abatacept treated patients to inform the design of future prospective, randomized studies.
- Mechanistic and biomarker studies with a focus on pharmacokinetics, receptor occupancy, T cell subsets (Tregs), donor cf-DNA, and blood transcriptomic profiles.

2. Background and Rationale

2.1. Background and Rationale for Investigational Product

Kidney transplantation for end-stage renal disease (ESRD) patients is associated with increased quality of life and reduced mortality compared with dialysis. Approximately 24,000 kidney transplants are performed in the United States annually. In contrast to sustained improvements in early post-transplant outcomes, much less progress has been made with long-term outcomes. Improvement of long-term outcomes remains an important goal. Long-term immunosuppressive therapy is necessary to prevent rejection, but toxicity associated with the most frequently used immunosuppressive drugs - particularly calcineurin inhibitors (CNIs) such as tacrolimus or cyclosporine - can ultimately lead to decreased renal function and result in the need for re-transplantation or return to dialysis. CNIs also increase the rates of serious post-transplant complications through associated metabolic and cardiovascular toxicities, including diabetes mellitus, hypertension, and hyperlipidemia.

Belatacept (Nulojix), a member of a novel class of immunosuppressive medications known as selective T-cell costimulation blocking agents, is an FDA approved alternative to CNI therapy for prophylaxis of kidney rejection in adults with 7-year outcomes data demonstrating significantly improved renal function, reduced risk of patient death, reduced risk of graft loss, and more favorable metabolic profile compared to CNI therapy (1). Additionally, belatacept more effectively blocks humoral responses that can lead to chronic injury and premature renal allograft failure. However, there are clinical and logistical barriers to broad adoption of belatacept. Studies have observed higher rates of early acute rejection (2), although our center has reduced acute rejection rates to standard levels by combining belatacept with transient, short-term CNI therapy (3). The logistical challenges related to the intravenous formulation of Belatacept and the requirement for costly, indefinite – likely life-long – monthly infusions has been problematic for both patients and infusion center capacity planning and scheduling. In the COVID-19 era, the requirement for in-person attendance and social distancing at infusion centers struggling to meet prior clinical demands as well as COVID-19 specific infusion services has intensified these challenges.

A promising approach to address these concerns was noted during periods of belatacept shortage which intensified beginning in 2017. During these periods, our team has utilized abatacept, an earlier selective T-cell costimulation blocking agent which differs from belatacept by only two amino acids. Abatacept is approved for use in rheumatoid arthritis (RA) and other autoimmune conditions, as well as prophylaxis of acute graft-versus-host disease (GVHD). We have reported our experience using abatacept as rescue immunosuppression in nine CNI intolerant kidney transplant recipients (4). There was 100% patient and graft survival after conversion to abatacept. They received abatacept for a median duration of 82 months with stable, long-term renal allograft function, with only a single patient experiencing one cellular rejection episode that responded fully to treatment, and no apparent increase in severity or frequency of infections (4).

Conversion to abatacept during the early post-transplant period will facilitate close monitoring and early detection of infections, rejection, adherence issues, or metabolic or other postoperative complications of the transplant procedure and medications. In contrast, while post-transplant complication rates decrease by 12-24 months after transplant, clinical visits are less frequent for patients who are stable, making early detection and close monitoring more difficult for patients.

2.2 Rationale for Investigational Dose and Regimen

Abatacept and belatacept are both fusion proteins targeting the CD80/CD86 receptor, acting as selective T-cell costimulation blocking agents. The dose of abatacept chosen for this trial follows the maintenance subcutaneous dose administered in rheumatoid arthritis or psoriatic arthritis; this dose was also used for 16 months of the ~21 months of one of the CNI intolerant patients treated at our center (4).

The doses of all other immunosuppressive agents will otherwise follow the early post-transplant Emory belatacept transplant regimen incorporating low-dose tacrolimus (target tacrolimus whole blood trough

between 3-5 ng/ml), mycophenylate mofetil (or mycophenolic acid or azathioprine), and prednisone 5 mg per day.

Specifically, participants on a qualifying belatacept regimen, defined as the Emory standard of care belatacept regimen consisting of Belatacept (iv monthly), tacrolimus (po, trough target 3-5 ng/ml), mycophenolate mofetil (500-1000 mg po bid) and prednisone (5 mg po daily), will have their iv monthly belatacept changed to sc weekly abatacept. They will receive sc abatacept through week 52 (month 12) post-transplant. If stable on the abatacept regimen and the patient prefers to remain on the sc abatacept at the end of study (month 12 post-transplant), then they will be maintained on this regimen. If the patient does not want to continue the sc abatacept regimen, then they will be converted back to belatacept iv monthly and resume our preferred, standard of care regimen of belatacept, tacrolimus, mycophenolate mofetil and prednisone.

3. Study Design

3.1. Description of Study Design

This is a phase I, open-label, prospective, single-arm single center study evaluating the effectiveness and safety of abatacept as a replacement for belatacept early post-transplant in first-time renal transplant recipients. There is a single arm in this study: an Investigational (abatacept) group. Participants will be assigned to treatment regimen for the first 12 months after transplantation.

During periods of belatacept unavailability, our team has utilized its predecessor abatacept, which is available as a subcutaneous formulation, as rescue immunosuppression in 9 CNJ intolerant kidney transplant recipients (4). All nine patients experienced successful allograft salvage with 100% patient and graft survival (median 115 months) after conversion to abatacept. They received abatacept for a median duration of 82 months with stable, long-term renal allograft function, a single cellular rejection episode, and no clinically apparent protective immunity concerns. Hence our findings suggest that abatacept as conversion therapy in kidney transplant recipients may be a viable subcutaneous alternative to belatacept for long-term maintenance therapy to overcome logistical barriers derived from belatacept IV infusion requirements and enhance global uptake of costimulation blockade-based immunosuppressive strategies.

The holder of the IND for this study is [name] [REDACTED], MD. The IND number is 151377. Under Title 21 of the Code of Federal Regulations (21CFR §312.62) the investigator will maintain adequate records of the disposition of Abatacept, including the date and quantity of the drug received, to whom the drug was dispensed (participant-by-participant accounting), and a detailed accounting of any drug accidentally or deliberately destroyed. Records for receipt, storage, use, and disposition will be maintained by the study site. A drug-dispensing log will be kept current for each participant. This log will contain the identification of each participant and the date and quantity of drug dispensed. All records regarding the disposition of the investigational product will be available for inspection. The Emory Investigational Drug Services (IDS) will store the drug. They will dispense it to the research team. Our plan is for the research team to give the study drug to the research participant who will then self-administer. The research team will instruct the participant on how to administer the study drug on day of first dose. If they need further teaching, we will provide more instruction. When participant is comfortable with self-injection, we plan to supply the patient with enough study drug to last until Month 6 visit.

- Month 6 patient brings back needle box for drug reconciliation. They will be resupplied with study drug doses up to Month 12.
- Month 12 patient brings back needle box for drug reconciliation.

Schedule may be altered based on par level of study drug in IDS at time of resupply.

Adherence amongst the abatacept group will be monitored by visualization of the used auto-injectors by clinical research staff at designated study visits. Study subjects on abatacept will be asked to bring their used auto-injector syringes between study visits to the next visit to confirm compliance with the study drug. Additionally, a study drug administration diary will be maintained and verified at each study visit. If non-compliance is discovered by the clinical research team, this will be deemed a protocol deviation of medication non-adherence. If the non-adherence is deemed to pose a risk to the study subject or the integrity of the study as determined by the research team, the study subject will be converted back to standard of care with belatacept.

3.2. Primary Endpoint

Primary feasibility endpoint

The proportion of subjects who tolerate subcutaneous injections and are compliant with self-administration as measured by abatacept administration logs and autoinjector accountability.

Primary Effectiveness (alloimmunity) endpoint

This primary effectiveness endpoint is the proportion of participants who remain free of biopsy proven acute T-cell mediated rejection (aTCMR) or antibody-mediated rejection (ABMR) as defined by Banff criteria at or before 12 months after transplantation.

Primary Safety Endpoints

- The cumulative incidence of serious adverse events
- Incidence of serious infection of special interest (e.g. requiring hospitalization or prolonged therapy, including but not limited to treatment ≥ 20 days)
- Incidence of patients with CMV viremia stratified by magnitude (≥ 35 but $< 10,000$ or $\geq 10,000$)
- Incidence of patients with BK viremia stratified by magnitude (undetected, > 0 but $< 1,000$, $\geq 1,000$ but $< 10,000$ or $\geq 10,000 - 100,000$, $\geq 100,000$ or stratified by log, which is reported as a result)
- Incidence of any malignancy including PTLN

3.3. Secondary Endpoints

Additional Effectiveness Endpoint

- Proportion of subjects experiencing the composite outcome of death or allograft failure at or before 12 months after transplantation.
- Proportion of subjects with biopsy proven acute T-cell mediated cellular rejection (BP-aTCMR) within 12 months of transplantation.
- Proportion of subjects treated for rejection with any of the following: i) corticosteroids within 12 months, ii) T-cell depleting therapy within 12 months, iii) any other treatment for rejection within 12 months of transplantation
- Proportion of subjects treated for acute rejection due to clinical suspicion rather than BP-aTCMR or BP-aABMR) within 12 months of transplantation.

- Proportion of subjects with biopsy proven active antibody mediated rejection (BP-aABMR) within 12 months of transplantation.
- Proportion of subjects and time to event for the changes in allograft biopsies for the 5 categories of aTCMR specified in the Banff schema.
- Proportion of subjects who develop de-novo donor specific antibody by 12 months
- Change in eGFR between abatacept initiation and 12 months after transplant.
- Days to events (TCMR, ABMR, de-novo DSA formation, graft loss).

3.4 Exploratory Endpoints

Clinical

Patient preferences and attitudes toward subcutaneous and intravenous route of administration will be assessed based on questionnaires administered at enrollment and at study visits at month 6 and 12 post initiation of Abatacept.

Immunologic/Mechanistic

- CD86 receptor occupancy on PBMC will be assessed before the initial dose of abatacept, and prior to abatacept administration at months 9, and 12 months post-transplantation.
- The incidence and breadth of anti-HLA antibody (including DSA) development over time (evaluated at screening, 3, 6 and 12 post-transplant). <note in the SOE within 30days>
- Peripheral blood T and B cell subsets will assessed at 6, 9, and 12 months post-transplant transplant may fall before inclusion window).

4. Selection of Participants and Clinical Sites/Laboratories

4.1 Rationale for Study Population

As currently practiced, kidney transplantation provides outstanding 1 year patient and transplant survival. However, long term results remain suboptimal. Renal transplantation does not restore normal life expectancy to recipients. While calcineurin-inhibitor based immunosuppression regimens have been pivotal in achieving short-term success their narrow therapeutic window is seen as an impediment to overcoming barriers to long-term success, including cardiovascular-, metabolic- and nephro-toxicities, as well as break-through donor-specific antibody formation. As described in the xx section belatacept, a T cell costimulation-blocker improved GFR, and lowered death and graft loss at seven years. However, post-approval use of belatacept remains low. Barriers to utilization include concern over increased rates of rejection, a gap in drug availability and the challenges associated with short and long-term administration of intravenous medications to transplant recipients. While strategies to reduce rejection rates while preserving the benefits of improved renal function and reduced DSA have been reported, the logistical barriers remain. Abatacept, a similar costimulation blocker has been successfully used as rescue immunosuppression for kidney transplantation. Abatacept has both subcutaneous and intravenous formulations. The goal is to explore the feasibility/efficacy of conversion from intravenous belatacept to subcutaneous abatacept to aid in the design of larger trials to study abatacept as part of an immunosuppression for kidney transplant recipients.

4.2 Enrollment

The study team will approach potential enrollees shortly after transplantation. Study staff will provide information about the trial including the consent form, to interested patients.

4.3 Inclusion Criteria

Individuals who meet all of the following criteria are eligible for enrollment as study participants:

1. Must be able to understand and provide informed consent.
2. Male or Female, 18-70 years of age at the time of enrollment (all races and ethnicities).
3. Negative crossmatch (virtual or physical) at time of transplant.
4. First dose of Study Drug must be given no less than 8 weeks, no more than 20 weeks post-transplant.
5. First time renal transplant who has been treated with belatacept from the time of transplant, receiving tacrolimus (target trough 3-5 ng/ml), mycophenylate mofetil (or mycophenolic acid or azathioprine), prednisone (also see exclusion criteria).
6. eGFR ≥ 40 ml/min/m² (using 2021 CKD-EPI equation).
7. Must have prior documented evidence of EBV seropositivity.
8. Female study participants of childbearing potential must have a negative pregnancy test on Day 0 prior to receiving the first dose of study drug.
9. Agreement to use contraception; according to the FDA Office of Women's Health (<http://www.fda.gov/birthcontrol>), there are a number of birth control methods that are more than 80% effective. Female study participants of child-bearing potential and men must consult with their physician and determine the most suitable method(s) from this list to be used from the time that study treatment begins until after study completion.
10. Vaccines up to date as per DAIT guidance for patients in transplant trials. (Refer to Appendix 2: DAIT Vaccine Guidance for Patients in Interventional Adult Transplant Trials)

11. Study participants must have a negative purified protein derivative (PPD) or negative testing for tuberculosis using an approved IGRA blood test, such as QuantiFERON®-Gold TB or T-SPOT-TB assay. PPD or IGRA testing must be documented to have been performed within the 52 weeks before enrollment. Patients with latent TB may become eligible according to local or national guidelines following completion of treatment.

4.4 Exclusion Criteria

Individuals who meet any of these criteria are not eligible for enrollment as study participants:

1. Inability or unwillingness of a study participant to give written informed consent or comply with study protocol.
2. Recipient of previous organ transplant of any type.
3. Multi-organ transplant.
4. cPRA >80 at time of enrollment.
5. History of any episode of biopsy-proven Banff rejection (including borderline rejection or any grade of acute TCMR) prior to enrollment.
6. History of any malignancy including lymphoma within 5 years of enrollment. Study participants with curatively treated non-melanomatous skin cancer or curatively treated cervical carcinoma in situ may be enrolled.
7. Any past or current issue which in the opinion of the investigator may pose additional risks to the participant in the study, may interfere with the study participant's ability to comply with the study requirements or that may impact the quality or interpretation of the data obtained from the study.
8. Human immunodeficiency virus (HIV): individuals known to be HIV positive.
9. Hepatitis C virus: any study participant who receives a kidney from a seropositive or HCV RNA PCR positive donor is ineligible. Any study participant who was HCV RNA PCR positive at transplant is ineligible. Any study participant with a history of HCV seropositivity or HCV infection who has not met criteria for sustained spontaneous clearance or sustained viral response to therapy is ineligible.
10. Hepatitis B virus: Individuals with any of the following are NOT eligible:
 - Recipient or donor positive for hepatitis B surface antigen (HBsAg)
 - Recipient or donor positive for antibodies to hepatitis B core antigen (anti-HBc)
 - Recipient or donor known to have had a positive HBV DNA PCR
11. Evidence of CMV viremia or clinical CMV infection at any time after transplant.
12. Kidney recipients who were CMV seronegative who received an organ from a CMV seropositive donor.
13. BK viremia of greater than 4.3 DNA log copies/ml (greater than 20,000 copies/ml) at any time post-transplant.
14. Active uncontrolled infection within 1 month of enrollment.
15. Clinically significant proteinuria (urinary protein/Cr ratio >1.0).
16. Receiving belatacept at a dose other than 5 mg/kg body weight.
17. Receiving mycophenolate mofetil at a dose of less than 1000 mg po QD (or mycophenolic acid or azathioprine equivalent).
18. Receiving prednisone at a dose greater than 5 mg po qd.
19. Presence of donor specific antibody by Luminex single antigen bead assay.

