Acute Rejection	A clinical and histologic event that meets the Banff 2017 revised criteria for acute cellular rejection.
Antibody Mediated Rejection	A clinical and histologic event that meets the Banff 2017 revised criteria for antibody mediated rejection.
Banff 2017 Scoring Criteria (Kidney)	
Reference & further details given in Roufosse C, et al. A 2018 Reference Guide to the Banff Classification of Renal Allograft Pathology. Transplantation 2018; 102: 1795-1814.
 
https://banfffoundation.org/wp-content/uploads/2019/01/A_2018_Reference_Guide_to_the_Banff_Classification.14-1.pdf
 
Category 1: Normal biopsy or nonspecific changes
 
Category 2: Antibody-mediated rejection Active ABMR Chronic, active ABMR C4d Staining without Evidence of Rejection
 
Category 3: Borderline changes Suspicious (Borderline) for acute TCMR
 
Category 4: T-cell-mediated rejection (TCMR) Acute TCMR (Grade IA, IB, IIA, IIB, III) Chronic Active TCMR (Grade I1, IB, II)

Donor Specific Antibodies	The presence of antibodies against antigens encoded by the HLA (human leukocyte antigen) complex that are expressed on the donor allograft.
Empirically treated rejection	Initiation of any treatment for rejection (e.g. steroids 10mg/kg or Thymoglobulin).
Graft Failure/Loss	
Graft loss occurs when a graft is deemed irreversibly nonfunctional and is the earliest of the day that:
 
 • dialysis which continues for six consecutive weeks is begun, or • a transplant nephrectomy is performed, or • The participant is re-listed for kidney transplantation, or • Has an eGFR <15 for a period of 8 weeks.
Modified Intent-to-Treat Sample	All enrolled participants who receive at least a single dose of the study intervention (abatacept)
Investigational Agent	Abatacept ORENCIA®
Lost to Follow-up	Missing in-person follow-up visits and cannot be reached by telephone or mail.
NIAID Medical/Scientific Observer	NIAID staff who regularly meets with the protocol director/principle investigator and study team including sponsor-appointed medical monitor, to review the progress of the study, safety events, and reporting.
NIAID Project Manager	NIAID staff who coordinates key study activities, including maintaining versions of protocols and amendments, informed consent templates, study management calls with investigators, coordinators, and other study personnel.

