7.5 Treatment of Allograft Rejection

Subjects suspected of having a rejection episode on the basis of clinical signs, symptoms or on the basis of laboratory tests will have a transplant biopsy. The local pathologist will make rejection diagnoses. Any rejection diagnosis detected on any biopsy will be treated per local practice taking into account the Banff score, degree of allograft dysfunction (and/or degree or rate of change in function) and recipient co-morbidities and clinical status. If rejection is clinically suspected and treatment for rejection is administered without biopsy confirmation, this will be considered an episode of clinically treated acute rejection (CTAR). CTAR events will be collected in case report forms.

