12.6. Study Stopping Rules

Study enrollment will be suspended pending expedited review of all pertinent data by the institutional review board (IRB), the NIAID medical/scientific observer, and the NIAID Data Safety Monitoring Board (DSMB), if any unexpected, fatal, or unanticipated life-threatening AE that is possibly or definitely related to the study treatment regimen or procedures.

Continuous Monitoring of Specific Events

Satisfaction of any of the following stopping rules at any time during the post-transplant follow-up will trigger an ad hoc DSMB Safety Review.

- Any unexpected fatal, or unanticipated life-threatening adverse event that is possibly or definitely related to the study treatment regimen or procedures
- 2 Deaths
- 2 Graft losses
- 2 Incidences of BP-aTCMR Banff IIB or Banff III
- 2 malignancies or life-threatening infections
- 4 rejections in total (biopsy-proven or empirically treated)

In addition to mandated stopping rule thresholds noted, NIAID DSMB, NIAID, or the study NIAID medical/scientific observer may pause enrollment after any single death, graft loss, Banff II, Banff III, malignancy or life-threatening infection event.

13. Safety Monitoring and Reporting

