14.2.3 Analyses of Secondary and Other Endpoint(s)

Additional Effectiveness Endpoints

- Proportion of subjects experiencing the composite outcome of death or allograft failure at or before 12 months after transplantation.
- Proportion of subjects with biopsy proven acute T-cell mediated cellular rejection (BP-aTCMR) within 12 months of transplantation.
- Proportion of subjects treated for rejection with any of the following: i) corticosteroids within 12 months, ii) T-cell depleting therapy within 12 months, iii) any other treatment for rejection within 12 months of transplantation.
- Proportion of subjects treated for acute rejection due to clinical suspicion rather than BP-aTCMR or BP-aABMR) within 12 months of transplantation.
- Proportion of subjects with biopsy proven active antibody mediated rejection (BP-aABMR) within 12 months of transplantation.
- Proportion of subjects and time to event for the changes in allograft biopsies for the 5 categories of aTCMR specified in the Banff schema.
- Proportion of subjects who develop de-novo donor specific antibody by 12 months
- Change in eGFR between abatacept initiation and 12 months on treatment.
- Days to events (TCMR, ABMR, de-novo DSA formation, graft loss)

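### Two treated-rejection secondary endpoints count from transplantation, so an empirical rejection treatment given on belatacept, which Exclusion 5 does not bar, could be reported as an abatacept outcome

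*Combined protocol and SAP*

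**What the plan says.** **Eligibility.** Exclusion 5 (synopsis and Section 4.4) bars "History of any episode of biopsy-proven Banff rejection (including borderline rejection or any grade of acute TCMR) prior to enrollment". No criterion names rejection that was treated without a biopsy. The nearest objective criterion is Exclusion 18, "Receiving prednisone at a dose greater than 5 mg po qd", which tests the current dose only. Exclusion 7 lets the investigator refuse a patient for any past issue that may add risk "or that may impact the quality or interpretation of the data obtained from the study".

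**Definitions.** The plan treats unbiopsied, treated rejection as an event in its own right. The definitions table ahead of Section 1 describes empirically treated rejection as "Initiation of any treatment for rejection (e.g. steroids 10mg/kg or Thymoglobulin"). Section 7.5 defines clinically treated acute rejection (CTAR) as the case "If rejection is clinically suspected and treatment for rejection is administered without biopsy confirmation".

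**Start of study drug.** Section 4.3: "First dose of Study Drug must be given no less than 8 weeks, no more than 20 weeks post-transplant".

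**Endpoints.** Sections 3.3 and 14.2.3 include "Proportion of subjects treated for rejection with any of the following: i) corticosteroids within 12 months", followed by T-cell depleting therapy and any other treatment for rejection, within 12 months of transplantation. The next item is the proportion treated on clinical suspicion rather than on a biopsy finding, over the same window. Section 14.4 summarises binary endpoints occurring up to 12 months post-transplant and sets no start at first dose.

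**Stopping rule.** Section 12.6 triggers an ad hoc DSMB review at "4 rejections in total (biopsy-proven or empirically treated"), at any time in post-transplant follow-up.

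**The concern.** The trial has one arm and no comparator, so whatever falls inside the endpoint window is read as the result of the abatacept regimen. Here the window opens 8 to 20 weeks before the regimen does. For biopsy-proven rejection, Exclusion 5 closes most of that gap by removing patients with an earlier episode. For rejection treated without a biopsy nothing objective closes it, although the plan defines that event and reports it in two secondary endpoints.

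At stake is the attribution of two descriptive proportions that are meant to inform later trials. With 18 patients, one misattributed episode changes the reported result from none to some.

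The same missing start date makes the four-rejection rule unclear. If an earlier episode counted, fewer on-study rejections would trigger a review, and Section 13.8.2.2.1 halts enrolment whenever an ad hoc review is required.

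**Working it through.** **1. The plan's own figures.** Section 13.9 tabulates binomial probabilities for n = 18. With P(0) = (1 − p)^18, the results are 0.397 at 5%, 0.150 at 10% and 0.054 at 15%. P(3+) is 0.058, 0.266 and 0.520. These round to the tabulated values, as do the 1+ and 2+ columns (all 12 entries). The table is sound, and the same binomial calculation is used below.

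**2. Share of the endpoint window before abatacept.** The first dose is at week 8 to 20 and the window is 52 weeks. 8/52 = 15.4% and 20/52 = 38.5%.

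**3. Can such a patient enter?** Take a hypothetical patient treated for suspected rejection at week 4 without a biopsy, and back on prednisone 5 mg with qualifying eGFR and no donor-specific antibody by week 10.

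| Criterion | Does it exclude? |
|---|---|
| Exclusion 5 (biopsy-proven rejection) | No, there was no biopsy |
| Exclusion 18 (current prednisone dose) | No, the course is complete |
| Exclusion 19 (donor-specific antibody) | No |
| Inclusion 6 (eGFR) | No |
| Exclusion 7 (investigator opinion) | Possibly, at discretion |

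**4. Would the episode be counted?** Sections 3.3, 14.2.3 and 14.4 put it inside the window. The mITT definition in 14.2.1 selects people, not event dates. Elsewhere the plan does anchor to study drug: adverse events are collected from the start of investigational treatment (13.4.1), and eGFR change runs from abatacept initiation (3.3, 14.2.3). No such anchor is given for these two endpoints.

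**5. Effect on the reported proportions.** Section 14.4 specifies the Wilson score interval with continuity correction. With z² = 3.84, n = 18, p = x/n and q = 1 − p:

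- lower = [2np + z² − 1 − z√(z² − 2 − 1/n + 4p(nq + 1))] / [2(n + z²)], set to 0 when x = 0
- upper = [2np + z² + 1 + z√(z² + 2 − 1/n + 4p(nq − 1))] / [2(n + z²)]

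For x = 1, the lower limit is (2 + 3.84 − 1 − 4.71)/43.68 = 0.003 and the upper limit is (2 + 3.84 + 1 + 5.99)/43.68 = 0.294. For x = 0, the upper limit is (3.84 + 1 + 4.71)/43.68 = 0.219.

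| Earlier episodes, none on abatacept | Counted from transplant | Counted from first dose |
|---|---|---|
| 1 patient | 1/18 = 5.6% (0.3 to 29.4) | 0/18 = 0% (0 to 21.9) |
| 2 patients | 2/18 = 11.1% (1.9 to 36.1) | 0/18 = 0% (0 to 21.9) |

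**6. How likely is at least one?** The documents give no rate. At assumed per-patient rates of 2%, 5% and 10%, 1 − (1 − p)^18 gives 30%, 60% and 85%.

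**7. Stopping rule, if an earlier episode counted.** With one carried over, three on-study rejections would reach the threshold instead of four. At an assumed 10% rate and at most one rejection per patient, P(3+ of 18) = 0.27 against P(4+ of 18) = 0.10. At 5% the pair is 0.058 and 0.011; at 15% it is 0.52 and 0.28.

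**The case against.** The strongest reply is that the collection text looks forward. Section 5.4.1 speaks of monitoring enrolled subjects for empirically treated rejection. Section 7.5 defines CTAR for study subjects and records it in case report forms. Section 9.3 assesses rejections at each study visit. Appendix 1, footnote 1, says visits before enrolment do not apply. An episode before enrolment might therefore never be entered. This stands in part: the plan does not make it certain that such an episode is scored. It does not remove the problem, because the endpoint definitions still include the period and the result would then depend on what happened to be entered.

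Second, Exclusion 7 can keep such a patient out, and study personnel review the medical record for eligibility (9.1). That narrows the gap, but a discretionary criterion does not close it. Section 7.5 also sends suspected rejection to biopsy, which makes unbiopsied treatment less likely. That text is written for study subjects, however, and itself allows for treatment without biopsy.

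Third, a biopsy-proven exclusion is objective and matches the primary endpoint, while barring everyone treated on suspicion would also remove patients who never had rejection. This is a fair defence of Exclusion 5. It means the counting rule is the essential repair, and the scope of the exclusion is for the sponsor to reconcile.

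A reader might infer that the primary effectiveness result is contaminated too. The documents do not support that for these episodes: the primary endpoint requires biopsy proof (3.2, 14.2.2). Nor is the days-to-events endpoint touched, since it lists TCMR, ABMR, de-novo donor-specific antibody and graft loss, and not empirically treated rejection.

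**Conclusion.** The point holds for two secondary endpoints. As defined, they include 8 to 20 weeks on belatacept, and no objective criterion removes patients treated for rejection without a biopsy in that time. Such an episode could therefore be reported as an abatacept outcome. It would be too strong to say that it will be: that depends on whether such a patient enters, whether Exclusion 7 is used, and whether the episode is recorded.

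The size is 5.6 percentage points per affected patient on both proportions. The expected number of affected patients is unknown, and the 2 to 10% rates used above are assumptions. The effect on the four-rejection rule is an ambiguity in the text and not a demonstrated error.

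**What to change.** In Sections 3.3, 14.2.3 and 14.4 (and the synopsis), state that the two treated-rejection endpoints count events from the first abatacept dose to 12 months post-transplant. List treatment for suspected rejection before that dose separately, as baseline history.

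Two items are for the sponsor to settle:
- Reconcile Exclusion 5 with the definitions of empirically treated rejection and CTAR, and say whether leaving these episodes out is intended.
- Clarify in Section 12.6 whether episodes before the first dose count toward the four rejections.

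The cost is a wording amendment and a dated baseline field in the case report form. Sample size and visits do not change, and the counting rule leaves eligibility as it is. One consequence should be stated in the report: time at risk becomes 52 − 20 = 32 to 52 − 8 = 44 weeks per patient, so these proportions are no longer full 12-month rates from transplant.
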